### 1.2.5 Novel Tumor Assessment and Psychometric Testing

In addition to the antitumor therapy, this protocol will in a preliminary manner assess novel measures of response and predictors of disease recurrence based on important recent advances in the diagnosis of AR-PCNSL. Based on the finding that essentially all AR-PCNSL are EBV associated, RT-PCR detection of EBV in the CSF has been found to be a sensitive and specific marker for lymphoma in HIV-infected patients with focal brain lesions. In combination with SPECT thallium or fluoro-2-deoxy-d-glucose positron emission tomography (FDG-PET) scanning of the brain, a minimally invasive diagnostic procedure for AR-PCNSL appears feasible. The combination of positive EBV PCR in the CSF and positive SPECT thallium has been shown to have 100% positive predictive value for lymphoma in AIDS patients with cerebral mass lesions. Likewise, if both tests are negative, the negative predictive value for lymphoma is 100%. Discordant findings require biopsy or persistent growth in the presence of anti-toxoplasmosis therapy in order for an empiric lymphoma diagnosis to be made. While minimally invasive approaches to defining focal brain lesions has gained acceptance and is considered an acceptable standard of care for initiation of specific therapy in AR-PCNSL in certain settings, the use of these studies have not been studied in terms of tumor response to therapy or in the relapsed setting. Also, the peripheral blood EBV loads have not been well correlated with AR-PCNSL, though there is evidence that the peripheral EBV load is

elevated in the setting of AR-PCNSL. Thus, study of EBV in the spinal fluid and plasma before, during and after treatment may provide preliminary information that can be useful for developing additional measures to assess tumor response (e.g. relatively non-invasive measures of minimal residual disease) and could provide a means toward predicting durability of response. Along with the more standard response assessments utilizing MRI and FDG-PET used in brain lymphoma, serial EBV DNA quantitation by PCR of the CSF and plasma will be used to provisionally assess response in correlation with the other standard outcome measures.

Neurocognitive preservation is central to the goals of this clinical investigation, and serial neuropsychometric testing will be performed on patients. Since at the time of presentation patients are expected to have tumor related cognitive impairment, baseline neuropsychometric testing will be performed within the first two months of the time of complete tumor response. Repeat testing will be performed every 3 to 6 months up to 2 years following end of treatment, and then again at 3 years. Such measures have been found to be useful in PCNSL patients for assessing neurocognitive functioning over time.

The protocol will also assess patients from the standpoint of the underlying HIV infection. Since justification for pursuing non-radiation-based therapy is that HAART may improve survival such that patients live long enough to experience radiation-induced brain injury, patients with multidrug resistant HIV not amenable to suppression will not be eligible for the study, because a meaningful lasting immune recovery will not be feasible. Thus, immune parameters such as the CD4+ and CD8+ cell counts, HIV viral loads, HIV resistance mutations, and HAART adherence will be recorded. Patients who fail to maintain low HIV viral loads and as a consequence experience other HIV-related complications that can affect neurocognitive function will be censored as soon as this becomes evident, and such patients can be replaced, as discussed in the statistical section of the protocol.

#### 1.2.6 Summary of Study Direction

The intent of this protocol is to provide data regarding the feasibility and effectiveness of high-dose methotrexate with leucovorin and rituximab given with HAART from a small number of patients with AR-PCNSL who have a favorable prognosis from the standpoint of their HIV disease. A major focus is to determine if a majority are alive without substantial brain dysfunction at two years after diagnosis. If the trial is favorable, then the approach may be of interest for further development in the extramural multicenter setting. The NCI-sponsored AIDS Malignancy Consortium will be apprised of the results as the trial progresses, as this is the group in the United States most likely to be interested in pursuing further research in the area.

This protocol was originally conducted in conjunction with a protocol being conducted by NIAID investigators in collaboration with our group focused on diagnosis of CNS brain masses (Protocol Number 05-CC-0246, Principal Investigator

[name]) Patients diagnosed with AR-PCNSL were followed up to 24 months on the NIAID study. The NIAID investigators on that study are also associate investigators on this study. Although 05-CC-0246 has since closed, we continue to collaborate with NIAID investigators, and patients may be concurrently enrolled in 06-C-0051 and appropriate NIAID protocols. Continued collaboration comprises a comprehensive diagnostic and treatment research effort that is intended to help foster further collaborative research and improved ability to study this disease in the extramural NIAID and NCI communities.

## **2 ELIGIBILITY ASSESSMENT AND ENROLLMENT**

### **2.1 ELIGIBILITY CRITERIA**

#### 2.1.1 Inclusion Criteria

2.1.1.1 Positive HIV serology (previous records acceptable)

2.1.1.2 Diagnosis of Primary Central Nervous System Lymphoma

2.1.1.3 Confirmed histopathologic diagnosis by NCI Laboratory of Pathology

2.1.1.4 If tissue diagnosis is not feasible for any reason, such as undue risk to the patient to acquire tissue diagnosis, the following will be accepted as confirmed AR-PCNSL diagnosis:

- Positive brain FDG-PET and
- EBV detected in the CSF using PCR

2.1.1.5 Age 18 years or greater

2.1.1.6 ECOG performance 0-4

2.1.1.7 Ability to understand and willing to provide informed consent

2.1.1.7.1 If patient unable to understand informed consent, a previously designated durable power of attorney for healthcare or an individual with legal authority may substitute in this capacity

2.1.1.7.2 Assignment of a durable power of attorney for healthcare if not already done

#### 2.1.2 Exclusion Criteria

2.1.2.1 Prior therapy for CNS lymphoma

2.1.2.1.1 Steroids not an exclusion

2.1.2.2 Evidence of lymphoma outside of the central nervous system

2.1.2.2.1 Ocular involvement will not exclude

2.1.2.3 Multidrug resistant HIV not amenable to long-term suppression based on either or both:

2.1.2.3.1 Clinical history of poor adherence to multiple antiretroviral drugs deemed sufficient to render effective HIV control unattainable;

2.1.2.3.2 HIV mutational analysis (genotyping and/or phenotyping) that reveals high-level resistance such that a combination regimen comprised of agents from at least two drug classes cannot be devised to suppress HIV long-term.

2.1.2.3.3 Refusal to adhere to HAART

2.1.2.4 Concurrent malignancy other than Kaposi sarcoma, resectable squamous cell or

- basal cell skin cancer, or T1 anal cancer amenable to surgical resection.
- 2.1.2.5 Heart failure, Class IV by New York Heart Association criteria
- 2.1.2.6 Chronic Liver Disease, Child-Pugh class B or C
- 2.1.2.7 Pregnancy
- 2.1.2.8 Refusal to practice contraception during chemotherapy.
- 2.1.2.9 Any condition or set of circumstances that the Principal Investigator (PI) or Lead Associate Investigator (LAI) interprets as creating undue risk to the patient by participating on this study or would make the patient unlikely to comply with the study.

## **2.2 RESEARCH ELIGIBILITY EVALUATION**

### **2.2.1 Screening Studies**

All radiographic studies and EKG must be completed within 3 weeks prior to study entry; all standard laboratory tests must be done within 72 hours prior to entry; tumor diagnostic studies and viral studies may be done at any time prior to entry)

- 2.2.1.1 History and physical examination with documentation of abnormal findings
  - 2.2.1.1.1 Evaluation of ECOG status
  - 2.2.1.1.2 Detailed history of antiretroviral therapy and assessment for potential multidrug resistant HIV
  - 2.2.1.1.3 HIV genotyping and/or phenotyping if needed to assess for HIV resistance (previous outside reports adequate if done within prior 6 months)
- 2.2.1.2 Brain Imaging Studies
  - 2.2.1.2.1 MRI scan
  - 2.2.1.2.2 FDG-PET scan
  - 2.2.1.3 Computed tomography scans of the chest abdomen and pelvis to assess for peripheral lymphoma
- 2.2.1.4 Cerebrospinal fluid studies (if previously performed on sister NIAID protocol, not necessary to repeat)
  - 2.2.1.4.1 Cytopathological examination
  - 2.2.1.4.2 Flow cytometric examination
  - 2.2.1.4.3 Measurement of cell count with differential, glucose and protein
  - 2.2.1.4.4 Quantitative EBV PCR (CC Microbiology)
  - 2.2.1.4.5 Ig PCR and EBV PCR (Molecular Pathology, [name], 2N116-A)
- 2.2.1.5 Brain Biopsy at site of tumor
  - 2.2.1.5.1 May be omitted if unsafe and if FDG-PET and EBV studies are positive
- 2.2.1.6 Serum creatinine
  - 2.2.1.6.1 Calculated and/or measured creatinine clearance
- 2.2.1.7 Complete blood count and differential
- 2.2.1.8 PT and PTT
- 2.2.1.9 Biochemical assessment
  - 2.2.1.9.1 Serum electrolytes

2.2.1.9.2 Hepatic panel

2.2.1.9.3 Mineral panel

2.2.1.10 EKG

2.2.1.11 HIV serology if previous records not available

2.2.1.12 Obtaining consent from a patient without capacity

When a subject does not have the capacity to give informed consent to enroll in this protocol, consent may be obtained from the subject's legal guardian or the subject's durable power of attorney for health care. In these cases, assent will be obtained if the subject is capable of providing it, and the subject's dissent will be respected.

Typically, the surrogate must be present to give informed consent. In exceptional cases, when it is not feasible for the surrogate to come to the Clinical Center, surrogate consent may be obtained by telephone. When this approach is used, a copy of the consent form will be provided to the surrogate ahead of time. In addition, a copy of legal guardianship papers, patient's durable power of attorney for health care, or documentation that the individual has legal authority will be placed in the patient's chart.

At the beginning of the call, the surrogate will be asked to identify themselves and confirm that they are the subject's legal guardian or hold the subject's durable power of attorney, and that they have the written consent form with them. The study, including the purpose, risks, potential benefits, and alternatives will be explained by a member of the Clinical Investigator from the research team who is authorized to obtain informed consent for the study. The surrogate will be offered the opportunity to ask any questions, and to deliberate and discuss with other parties before making a decision. If the surrogate wants more time, a second call will be arranged.

The conversation will be monitored by a third party at the Clinical Center who is not a member of the research team (e.g. nurse, social worker, bioethics). The surrogate will be asked to sign the consent form, retain a copy, and mail the original to the research team. An explanation of the circumstances and manner of obtaining the surrogate's consent, the names of the person providing consent, the person obtaining consent, and the monitor, will be documented in a progress note in the subject's medical record, and signed and dated.

When surrogate consent is obtained by telephone, the research team will establish a reliable means of communicating with the surrogate regarding future decisions, and will consider the possibility of having someone present at the Clinical Center to make day-to-day decisions on the patient's behalf. At the time of continuing review, the research team will provide the IRB with a summary of the instances in which telephone consent was used, and the justifications for using it.

## 2.3 REGISTRATION PROCEDURES

Each patient will be discussed with the Principal Investigator or Lead Associate Investigator, or other designated Associate Investigator. Once it has been determined that a patient qualifies, informed consent will be obtained from the patient, as documented by a signed statement of informed consent approved by the NCI-IRB.

Authorized staff must register an eligible candidate with NCI Central Registration Office (CRO) within 24 hours of signing consent. A registration Eligibility Checklist from the web site (<http://home.ccr.cancer.gov/intra/eligibility/welcome.htm>) must be completed and sent via encrypted email to: NCI Central Registration Office [[contact]](mailto:[contact]). After confirmation of eligibility at Central Registration Office, CRO staff will call pharmacy to advise them of the acceptance of the patient on the protocol prior to the release of any investigational agents. Verification of Registration will be forwarded electronically via e-mail to the research team. A recorder is available during non-working hours.

## 2.4 TREATMENT ASSIGNMENT

### Cohorts

Number	Name	Description
1	Single Cohort	HIV-infected, adult patients with AIDS-related primary central nervous system lymphoma

### Arms

Number	Name	Description
1	Single arm	Induction treatment cycles with rituximab, high-dose methotrexate and leucovorin will be administered every 2 weeks for 6 cycles. Two additional consolidation cycles of high-dose methotrexate without rituximab will be administered at 4 weeks and 8 weeks following completion of the combined therapy.

## 3 STUDY IMPLEMENTATION

### 3.1 STUDY DESIGN

The primary objective of this study is to estimate the fraction of patients with AR-PCNSL receiving experimental treatment consisting of HAART and rituximab combined with high-dose methotrexate and leucovorin who are alive and without recurrent lymphoma or severe cognitive problems at two years.

#### 3.1.1 Additional exclusion criteria that would prohibit use of high dose methotrexate

In order to receive the primary protocol therapy, patients must not have any of these additional exclusion criteria that would prohibit the use of high dose methotrexate:

[figure not shown]
##### 3.1.1.1 ECOG Performance Status = 4

##### 3.1.1.2 Laboratory abnormalities that make the protocol therapy unsafe to administer:

###### 3.1.1.2.1 Platelet count <50,000/mm^3

- 3.1.1.2.2 Inability to obtain an absolute neutrophil count  $>1000$  cells/mm^3 despite use of filgrastim for at least 5 days (see section 3.3.5.6)
- 3.1.1.2.3 ALT and/or AST  $>2$  X upper limit of normal unless due to antiretroviral therapy or other necessary medications, in which case ALT and AST exclusion cut-off is  $>5$ X upper limit of normal
- 3.1.1.2.4 Bilirubin  $>2$  X upper limit of normal unless due to protease inhibitor therapy
- 3.1.1.2.5 Creatinine  $>1.5$  mg/dL, unless estimated or measured creatinine clearance is  $\geq 60$  mL/min.
  - If creatinine clearance estimated with the method of Cockcroft and Gault is  $<100$  mL/min, a measured creatinine clearance should be obtained.
- 3.1.1.3 Patients with Class III or higher New York Heart Association Classification of Congestive Heart Failure unresponsive to treatment that would make hydration infeasible.
- 3.1.1.4 Evidence of other opportunistic diseases or complications of HIV infection that would make the protocol therapy infeasible to administer. Examples include, but are not limited to:
  - 3.1.1.4.1 Aggressive symptomatic Kaposi's sarcoma requiring systemic therapy
  - 3.1.1.4.2 Uncontrolled systemic and/or CNS-invasive fungal infection
- 3.1.1.5 Hypersensitivity to murine proteins or any component of rituximab
  - Patients who are ineligible to receive rituximab, high-dose methotrexate and leucovorin will be treated with "Radiation-sparing Best Available Care", as outlined in Section 3.6.

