**Design:** Phase II pilot study investigating high-dose methotrexate-rituximab given with leucovorin rescue and HAART as a treatment for AR-PCNSL. Evaluation will include quantitative measurement of lymphocyte subsets, quantitative polymerase chain reaction (PCR) of HIV and EBV viral loads (including both blood and cerebrospinal fluid in the case of EBV) to assess immune response and anti-viral effects. Tumor evaluation with brain magnetic resonance imaging (MRI) and brain fluoro-2-deoxy-d-glucose positron emission tomography (FDG-PET scans) will be used for staging and response assessment. Longitudinal neuropsychologic testing after complete responses are documented will serve to evaluate neurocognitive parameters post therapy. Chronic administration of HAART and longer-term evaluation of immune system parameters will be studied as part of an overall assessment of the therapy. Patients with AR-PCNSL who cannot receive high-dose methotrexate due to poor renal or cardiac function will receive HAART and “Radiation-Sparing Best Available Care”, generally consisting of dose-dense rituximab, and will be evaluated as a separate cohort for additional secondary endpoints.

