3.4.2 High-dose methotrexate

3.4.2.1 The creatinine clearance (CrCl) will be calculated by method of Cockcroft-Gault prior to each cycle (see [Appendix 4](#)). If CrCl is  $\geq 100$  mL/min, then no dose adjustment is necessary. If CrCl is  $< 100$  mL/min, then the methotrexate dose is adjusted by the fraction of CrCl less than 100 mL/min (e.g., methotrexate dose =  $6000 \text{ mg/m}^2 \times \text{CrCl}/100$ ).

3.4.2.1.1 For estimated creatinine clearance  $< 100$  mL/min, a 24-hour urine collection should be obtained *plus* a serum creatinine at the end of the collection period to determine a measured creatinine clearance.

3.4.2.2 Delayed methotrexate serum clearance ( $> 3$  days after methotrexate infusion) may occur and mandates accelerated rescue and continued hydration and alkalinization. The minimum interval between achieving a serum methotrexate level  $\leq 0.05 \text{ mcg/mL}$  and the start of a subsequent treatment cycle is 7 days.

3.4.2.3 For creatinine clearance  $< 60$  mL/min, no methotrexate will be administered. Administer rituximab without methotrexate after discussion with a medically responsible investigator if renal function cannot be expected to be optimized (CrCl  $\geq 60$  mL/min) within 3 days.

3.4.2.4 For transient ALT and/or AST elevations  $\geq 10X$  the upper limit of normal, withhold methotrexate until both ALT and AST are  $\leq 5X$  the upper limit of normal, then permanently reduce methotrexate dosage by 25% for all subsequent cycles beginning with the next cycle.

3.4.2.5 For ANC  $< 1000 \text{ cells/mm}^3$ , delay methotrexate until ANC recovers to  $\geq 1000/\text{mm}^3$ .

3.4.2.6 For platelet counts  $< 50,000/\text{mm}^3$ , delay methotrexate until platelet count recovers to  $\geq 50,000/\text{mm}^3$ .

3.4.2.7 For any other Grade 3 or greater toxicities related to methotrexate, with the exception of hematologic toxicity, hold methotrexate until toxicity abates to Grade  $\leq 2$ .

3.4.2.8 For pulmonary toxicity related to methotrexate, permanently discontinue methotrexate.

3.4.2.9 Note, if toxicity attributed to methotrexate prevents subsequent methotrexate treatment prior to the time of complete response, patient will be considered a treatment failure. Failure of toxicity to resolve and thus creating dose delays in excess of 15 days will result in methotrexate discontinuation.

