### **3.6 “RADIATION-SPARING BEST AVAILABLE THERAPY” FOR PATIENTS NOT ELIGIBLE FOR HIGH-DOSE METHOTREXATE IN THE PHASE II COHORT**

Patients with EBV+ AR-PCNSL that have co-morbidities prohibiting administration of high dose methotrexate will receive HAART combined with dose-dense rituximab unless there is a clinical reason that this should not be used or would not be considered best therapy, such as hypersensitivity to murine proteins.

Dose dense administration of rituximab increases serum concentration, which would be expected to allow for better distribution to the CNS. Patients will receive one 4-week cycle, consisting of a total of 6 doses of rituximab administered on Days 1, 3, 5, 8, 15, and 21.

Patients who are hypersensitive to murine proteins or any component of rituximab, or other clinical contraindications to using the dose-dense rituximab regimen, will receive HAART (See Section 3.6.2). If clinically indicated, additional chemotherapy or radiotherapy may be employed in such patients (See Section 3.6.3).

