### 3.6.1 Rituximab

#### 3.6.1.1 Rituximab 375 mg/m^2 IV days 1, 3, 5, 8, 15, and 21

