**Day 2:**

1. 7 am: notify MD of urine pH and hourly UOP. If UOP < 100mL/hour or urine pH <7 or >8, adjust IVF.
2. Methotrexate 6000 mg/m^2. Order within the 06-C-0051 CRIS order set. Include Sodium Bicarbonate 45mEq as an additive. (May be adjusted between 25-75mEq depending on individual patient needs).
  - a. For creatinine clearance 60-100 mL, adjust methotrexate dose using formula: (Creatinine Clearance)/100 x 6000 mg/m^2
  - b. For creatinine clearance < 60ml/min, methotrexate **will NOT be administered**.
  - c. If episodic AST/ALT elevation > 10X upper limit normal on previous cycle, decrease methotrexate by 25%
3. Goal Start time: administer methotrexate starting between 9:00-10:00 am

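### The renal exclusion in 3.1.1.2.5 depends on creatinine above 1.5 mg/dL, so a patient with clearance below 60 mL/min can pass the methotrexate entry list, and the text then gives two first regimens (wrong as written, minor).

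*Combined protocol and SAP*

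**What the plan says.** Section 3.1.1 sets the entry condition for primary therapy: "patients must not have any of these additional exclusion criteria that would prohibit the use of high dose methotrexate". The only renal item in that list is 3.1.1.2.5, creatinine above 1.5 mg/dL "unless estimated or measured creatinine clearance is" 60 mL/min or more. Its sub-bullet asks for a measured clearance when the Cockcroft-Gault estimate is below 100 mL/min, but attaches no cut-off. The general exclusions in 2.1.2 name no renal criterion.

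Three other places make clearance itself decisive:

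- **Appendix 9, Day 2** withholds the drug at any creatinine: "For creatinine clearance < 60ml/min, methotrexate" is not to be given.
- **Section 3.4.2.3** has the same threshold and adds a treatment instruction: "Administer rituximab without methotrexate after discussion with a medically responsible investigator if renal function cannot be expected to be optimized" to 60 mL/min within 3 days.
- **The Précis** sends "Patients with AR-PCNSL who cannot receive high-dose methotrexate due to poor renal or cardiac function" to HAART and Best Available Care as a separate cohort. Section 3.6 says that patients with "co-morbidities prohibiting administration of high dose methotrexate will receive HAART combined with dose-dense rituximab", and 3.6.1.1 gives the schedule: "IV days 1, 3, 5, 8, 15, and 21".

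The last bullet of 3.1.1.5 links the two: "Patients who are ineligible to receive rituximab, high-dose methotrexate and leucovorin will be treated with" Best Available Care.

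**The concern.** The entry list turns on creatinine and the dosing rules turn on clearance. A patient with creatinine of 1.5 mg/dL or less and clearance below 60 mL/min therefore passes the list for a cohort defined by a drug that the patient may not receive. Once there, 3.4.2.3 gives rituximab on day 1 of two-week cycles, while 3.6 gives six doses in 21 days. Section 3.6 justifies the denser schedule by the expectation of better distribution to the CNS.

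Three things are at stake:

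- **First treatment**, in a disease that the Précis describes as usually fatal within months.
- **Cohort membership.** The patient could be missing from, or late into, the cohort of up to 10 that serves objective 1.1.2.5.
- **Classification.** Nothing says outright how to count a main-cohort patient who never starts methotrexate because of pre-existing renal impairment.

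**Working it through.** **The plan's own figure.** Section 6.1.3 states 88% power for n = 15, 30% against 65%, one-sided exact test at 0.1. The smallest cut-off that holds the level is 8 successes: P(X ≥ 8 | 0.30) = 0.050, whereas 7 gives 0.131. Power is P(X ≥ 8 | 0.65) = 0.887, so the stated figure reproduces. The issue here is eligibility logic and does not alter it.

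**Logic of the list.**

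| Creatinine | Clearance | Excluded by 3.1.1.2.5? | Methotrexate allowed by 3.4.2.3 and Appendix 9? |
|---|---|---|---|
| >1.5 | ≥60 | no | yes |
| >1.5 | <60 | yes | no |
| ≤1.5 | ≥60 | no | yes |
| ≤1.5 | <60 | **no** | **no** |

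Only the last row is inconsistent.

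**Can a patient be in that row?** Appendix 4 gives clearance = (140 − age) × weight / (72 × creatinine), times 0.85 for women. Ages and weights below are my assumptions.

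- Man, 40 years, 60 kg, creatinine 1.5: 100 × 60 / 108 = 55.6 mL/min. He passes the list.
- Man, 40 years, 64 kg, creatinine 1.6: 100 × 64 / 115.2 = 55.6 mL/min. He is excluded, with the same clearance.
- Weight at which clearance equals 60 at age 40 and creatinine 1.5: 60 × 1.5 × 72 / 100 = 64.8 kg for a man; 64.8 / 0.85 = 76.2 kg for a woman.
- The same at creatinine 1.0: 60 × 1.0 × 72 / 100 = 43.2 kg and 43.2 / 0.85 = 50.8 kg.

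The gap is thus widest at creatinine 1.5 and narrows quickly below it. Section 4.12 says malnutrition is common in this disease, so low weights are plausible. How many patients would fall in the gap cannot be derived from the documents.

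**The two schedules.** Under 3.5.3 the main regimen stops if clearance cannot be corrected within 2 weeks, and 3.5.12 then permits, but does not require, dose-dense rituximab. As an upper illustration, assume the switch comes on day 15.

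| | Dose-dense from the start | 3.4.2.3 first, switch on day 15 |
|---|---|---|
| Dose days | 1, 3, 5, 8, 15, 21 | 1, then 15, 17, 19, 22, 29, 35 |
| Doses by day 14 | 4 | 1 |
| Doses by day 21 | 6 (6 × 375 = 2,250 mg/m²) | 4 (4 × 375 = 1,500 mg/m²) |
| Dose-dense course ends | day 21 | day 35 |

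**The case against.** The strongest reply is that the list is a necessary condition and not a sufficient one. Section 3.1.1 says who may not receive primary therapy; it does not say that everyone else must. Section 3.6 is mandatory and is triggered by whatever prohibits methotrexate, so a patient with fixed low clearance is already sent to Best Available Care. Section 3.4.2.3 sits under treatment modifications, works cycle by cycle and requires discussion with an investigator; under 2.3 each patient is also discussed before registration. This stands in part. It shows what the plan intends, but 3.4.2.3 still gives a different regimen for the same patient, and the list contains no clearance rule that would stop entry. Neither 2.1.2.9 nor 3.1.1.4 closes the gap: the first excludes from the whole study and assigns no cohort, and the second reaches renal disease only by judgement, as a complication of HIV.

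Other points stand. The two-week delay is a worst case: 3.5.3 does not require waiting when impairment is known to be irreversible, and 3.5.4 and 3.5.11 allow earlier stopping. Creatinine of exactly 1.5 is the edge of the gap. Appendix 4 itself lists malnutrition, muscle wasting and female sex among the situations where the estimate is inaccurate, so the measured value decides. Figure 1 covers eligibility evaluation and initial therapy, is not shown, and may state the rule.

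A reader might infer a threat to the primary analysis: one such patient counted as a failure under 5.3.6 or 3.10.1 would move the fraction by up to 1/15 = 6.7 points and lower power at 65% from 88.7% to P(Bin(14, 0.65) ≥ 8) = 81.6%. The documents do not support giving this weight. Section 6.1.3 counts evaluable patients as those who receive all treatment including high-dose methotrexate, which favours not evaluable and leaves the result unchanged. The discontinuation wording of 5.3.6 also fits poorly a patient who never started the drug.

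**Conclusion.** Wrong as written, minor. The renal exclusion is conditioned on the wrong variable: it admits patients with creatinine of 1.5 mg/dL or less and clearance below 60 mL/min to a cohort whose defining drug they may not receive, and the text then offers two first regimens.

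The effect is limited. A reader might infer an overdose risk; there is none, because 3.4.2.3 and Appendix 9 both block methotrexate below 60 mL/min. No change to the primary result is expected on the 6.1.3 wording. A delay to dose-dense rituximab is possible but not certain, and is at most about two weeks under 3.5.3; the dose counts above rest on the assumed day-15 switch. The weight thresholds rest on an assumed age of 40. The conclusion concerns the text only and would fall away if Figure 1 states a clearance rule. The second cohort is described in 6.1.3 as exploratory, so a misplaced patient there affects description and not inference.

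**What to change.** Amend 3.1.1.2.5 to exclude: *creatinine clearance <60 mL/min regardless of serum creatinine (measured value if the Cockcroft-Gault estimate is <100 mL/min), unless expected to be corrected to ≥60 mL/min within the 2 weeks allowed by 3.5.3*. State that excluded patients enter the Best Available Care cohort from the start.

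The window should be the two weeks of 3.5.3 and not the 3 days of 3.4.2.3. With a 3-day limit, a patient whose clearance would recover on, say, day 7 would be sent to Best Available Care, and the documents describe no route back to methotrexate. With the two-week window, 3.4.2.3 keeps its role for reversible impairment.

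The cost is one line. Clearance is already obtained at screening (2.2.1.6.1), a measured value is already called for below 100 mL/min, and sample size, alpha and power do not change. The small downsides are that assignment may wait for the 24-hour collection and that the investigator must judge reversibility at entry.
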